	
and who have no major protocol deviations expected to affect efficacy, immunogenicity, safety or reactogenicity assessments as determined by the Sponsor Medical Monitor or designee in a blinded manner.
 
• The PP analysis set will be analyzed according to which study vaccine was received in the event there is a discrepancy. PP analysis sets are defined for the following Phases of the study:
○ Phase 1 PP set: this excludes any participant that has evidence of SARS-CoV-2 infection at baseline or prior to the analysis time point concerned (IcEv3) or that receives an off-study COVID-19 vaccine prior to the analysis time point concerned (IcEv2).○ Phase 2/3a PP set: this pools data from Phase 2 and Phase 3a participants and excludes any participant that has evidence of SARS-CoV-2 infection at baseline or prior to the analysis time point concerned (IcEv3) or that receives an off-study COVID-19 vaccine prior to the analysis time point concerned (IcEv2).○ Phase 1/2/3a PP set: this pools data from Phase 1, 2 and Phase 3a participants and excludes any participant that has evidence of SARS-CoV-2 infection at baseline or prior to the analysis time point concerned (IcEv3) or that receives an off-study COVID-19 vaccine prior to the analysis time point concerned (IcEv2). This set will include evaluations of immunogenicity up to Day 92 only○ Phase 3b PP set: this excludes any participant with evidence of SARS-CoV-2 infection on Day 1 or up to 7 days after the 2nd study vaccination (IcEv3) or that receives an off-study COVID-19 vaccine prior to Day 92 (IcEv2)○ Phase 3c-1 PP set: this includes just the participants enrolled in the Phase 3c-1 subset of Phase 3c but excludes any participant that has evidence of SARS-CoV-2 infection at baseline or prior to the analysis time point concerned (IcEv3) or that receives an off-study COVID-19 vaccine prior to the analysis time point concerned (IcEv2)○ Phase 3c PP set: this includes all of Phase 3c but excludes any participant that has evidence of SARS-CoV-2 infection at baseline or prior to the analysis time point concerned (IcEv3) or that receives an off-study COVID-19 vaccine prior to the analysis time point concerned (IcEv2)○ Pooled PP set: this pools data from Phase 1/2/3a/3b and excludes any participant with evidence of SARS-CoV-2 infection on Day 1 or up to 7 days after the 2nd study vaccination (IcEv3) or that receives an off-study COVID-19 vaccine prior to Day 92 (IcEv2). This will include evaluations up to Day 92 only• Immunogenicity Analysis Set (IAS): Includes all participants who received all protocol required doses of study vaccine (ARCT-154 or placebo or ChAdOx1) up to the evaluation timepoint concerned,

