--	--

	
formula, if the incidence rate of an adverse event is 0.1%, the probability to detect one event in 1,200 vaccinated participants is 69.9% and, if the incidence rate is 1.0%, the probability is more than 99%:
 $p = 1 - (1 - R)^N$ 
where R = incidence rate and N = sample size
 
The primary immunogenicity noninferiority endpoint for Phase 3c is the ratio of geometric mean concentrations (geometric mean ratio or GMR) for neutralizing antibody (using the pseudovirus microneutralization assay [MNT]) concentration and will be evaluated in participants in the Phase 3c-1 Immunogenicity Analysis Set (Section 8.2). Sensitivity analyses will be performed in the Phase 3c PP set. International units (i.e., the WHO/NIBSC international reference standard) will be used if available.
 
The null hypothesis (H_0^{GMR}) for the primary endpoint is as follows:
 $H_0^{\text{GMR}}: R \leq \text{NIM}$ 
Where R is the ratio of GMC (i.e., GMC for ARCT-154 arm / GMC for the ChAdOx1 arm) and NIM is the acceptable noninferiority margin (0.67). The null hypothesis will be rejected if the lower bound of the 95% confidence interval for GMR is > 0.67.
 
Assuming a GMR of ≥ 0.9 and a coefficient of variation of 4.6, a sample size of 800 participants in Phase 3c-1 will provide greater than 90% power to exclude a non-inferiority boundary of 0.67 based on the use of a one-sided test at the alpha=0.025 level of significance, accounting for a dropout rate of approximately 20-25% due to the national COVID-19 vaccination campaign in Vietnam.
 
A sequential/hierarchical testing procedure will be used to control type 1 error rate over the Phase 3c primary endpoint and the secondary endpoints such that the secondary immunogenicity endpoints will only be tested if the null hypothesis is rejected for the primary endpoint and Phase 3c secondary endpoints numbers 1 through 5 will be tested sequentially using the same hierarchical test procedure with each endpoint only being tested if the null hypothesis is rejected for the preceding endpoint.
 
Missing Data
 
How missing data points will be handled will be described in the SAP.

--	--

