3.2 Phase 3b

3.2.1 Phase 3b Primary Objectives and Endpoints

The primary objectives and endpoints for Phase 3b are presented in [Table 5](#). These form the primary objectives and endpoints for the study overall.

Table 5 Phase 3b Primary Objectives and Endpoints

Phase 3b Primary Objectives	Endpoint Description
1. To assess the safety and reactogenicity of ARCT-154 compared to placebo	
Safety will be evaluated in all participants in the Phase 3b SAS and will be summarized for each vaccination as number and percentage of participants with:
 
• Any unsolicited AE starting within 28 days after each study vaccine administration, summarized by severity and relationship to study vaccine.• Any medically attended adverse event (MAAE), serious adverse event (SAE), or AE leading to discontinuation/withdrawal through Final Visit/Early Termination (ET) summarized by relationship to study vaccine. 
Reactogenicity will be evaluated in the Phase 3b RAS and will be summarized following vaccinations on Day 1 and Day 29 only as the number and percentage of participants with:
 
• Any solicited local or systemic AE starting within 7 days after each study vaccine administration by toxicity grade.
2. To evaluate the efficacy of ARCT-154 and placebo for the prevention of virologically confirmed COVID-19	
Efficacy will be evaluated in all participants in the Phase 3b mITT. The endpoint to be evaluated is as follows:
 
• The first occurrence of confirmed, protocol-defined (Appendix 2) COVID-19 with onset between Day 36 and Day 92 inclusive.

Abbreviations: AE=adverse event; COVID-19=coronavirus disease 2019; MAAE=medically attended adverse event; SAE=serious adverse event; ET=early termination

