Estimand 2	
The proportion of participants (and 95% confidence interval) with virologically confirmed COVID-19 (Appendix 2) detected after 7 days post the second study vaccine dose.Proportion of participants (and 95% confidence interval) with virologically confirmed COVID-19 detected at any time after first vaccine dose	Phase 3b mITT (primary) Phase 3c mITT (exploratory)	For deaths unrelated to COVID-19, censor at date of death. For participants who undergo Switchover/Further Study Vaccine or receive a non-study COVID-19 vaccine, censor at date of Switchover or non-study vaccination.	The proportion of participants with virologically confirmed COVID-19 (Appendix 2) in each vaccine group will be displayed together with 95% CI.	Sensitivity: the same analysis will be performed in the Pooled mITT and Phase 3b PP analysis sets.

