8.7.3.4 Main Estimation of Phase 3b Primary Efficacy Endpoint (Estimand 2)

This endpoint is the incidence rate of virologically confirmed COVID-19. The main analysis on this endpoint will be carried out in the Phase 3b mITT and the sensitivity analysis will be performed in the Phase 3b PP analysis set. Incidence rate in each arm will be displayed together with 95% CI.

The statistical hypothesis for this analysis is described in [Section 8.4.2](#).

Definition and handling of intercurrent events is described in [Section 8.3.1](#).

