- **Per-Protocol (PP) analysis Set:** Includes all eligible randomized participants who received all protocol-required doses of study vaccine (ARCT-154 or placebo) up to the evaluation timepoint concerned and within the protocol predefined window, and who have no major protocol deviations expected to affect efficacy (PP efficacy), immunogenicity (PP immunogenicity), safety or reactogenicity assessments as determined by the Sponsor Medical Monitor or designee in a blinded manner. The PP analysis set will be analyzed according to which study vaccine was assigned, in the event there is a discrepancy. PP sets will be further derived for efficacy and immunogenicity as follows:
  - **Efficacy**
    - Phase 3b PP efficacy set: includes per protocol Phase 1 participants and excludes any participant with evidence of SARS-CoV-infection on Day 1 up to 7 days after the 2nd study vaccination (IcEv3) or that receives an non-study COVID-19 vaccine prior to Day 92 (IcEv2).
    - Pooled PP efficacy set: includes per protocol Phase 1, 2, 3a and Phase 3b participants and excludes any participant with evidence of SARS-CoV-infection on Day 1 up to 7 days after the 2nd study vaccination (IcEv3) or that receives an non-study COVID-19 vaccine prior to Day 92 (IcEv2).
  - **Immunogenicity**
    - Phase 1 PP immunogenicity set: includes per protocol Phase 1 participants and excludes any participant with evidence of SARS-CoV-2 infection on Day 1 up to Day 57 (IcEv3) or who receives a non-study COVID-19 vaccine prior to the analysis time point concerned (IcEv2).
    - Phase 2/3a PP immunogenicity set: includes per protocol Phase 2 and Phase 3a participants and excludes any participant with evidence of SARS-CoV-2 infection on Day 1 up to Day 57 (IcEv3) or who receives a

non-study COVID-19 vaccine prior to the analysis time point concerned (IcEv2).

- Phase 1/2/3a PP immunogenicity set (or Phase 1/2 PP immunogenicity set): includes per protocol participants from Phase 1, 2 and Phase 3a participants and excludes any participant with evidence of SARS-CoV-2 infection on Day 1 up to Day 57 (IcEv3) or who receives an non-study COVID-19 vaccine prior to the analysis time point concerned (IcEv2). This set will include evaluations of immunogenicity up to Day 92 only. Of note, this analysis set will be restricted to Phase 1/2 participants for analysis of parameters not collected in phase 3a participants and will be referred to as Phase 1/2 PP immunogenicity set)

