PP immunogenicity sets will be derived up to the analysis time point concerned based on the availability of each assay. Three time points are considered:

- Up to Day 57
- Up to Day 92
- Up to Day 120

The following major protocol deviations are expected to affect efficacy and will lead to exclusion of a participant from the PP efficacy set:

- Received wrong study vaccine up to Day 92
- Did not receive study vaccine
- Received non-study COVID-19 vaccine (IcEv2) up to Day 92
- COVID-19 infection (positive RT-PCR or other COVID-19 test) up to Day 36
- Result of SARS-CoV-2 anti-nucleocapsid antibodies test is Positive/Undetermined up to Day 36

The following major protocol deviations are expected to affect immunogenicity and will lead to exclusion of a participant from the PP immunogenicity sets:

- Received wrong study vaccine up to the time point concerned
- Did not receive study vaccine
- Received non-study COVID-19 vaccine (IcEv2) up to the time point concerned
- Received confounding medication (IcEv5) up to the time point concerned
- COVID-19 infection (positive RT-PCR or other COVID-19 test) up to Day 57
- Result of SARS-CoV-2 anti-nucleocapsid antibodies test is Positive/Undetermined up to Day 57

All major protocol deviations listed above are conditions leading to exclusion from the PP set specified in the protocol.

- **Immunogenicity Analysis Set (IAS):** Includes all participants who received all protocol-required doses of study vaccine (ARCT-154 or placebo) up to the evaluation timepoint concerned, who have no evidence of prior SARS-CoV-2 infection (no positive RT-PCR or other COVID-19 test or seropositivity for anti-nucleocapsid antibody) up to Day 57 and who have at least 1 valid post-vaccination immunogenicity assay result.

All participants in the IAS will be analyzed according to which study vaccine was assigned.

IAS are defined for the following Phases of the study:

- Phase 1 IAS: this corresponds to data from participants in Phase 1
- Phase 2/3a IAS: this pools data from participants in Phase 2 and 3a
- Phase 1/2/3a IAS (or phase 1/2 IAS): this pools data from Phase 1, 2 and 3a participants and will include evaluations of immunogenicity up to Day 92 only. Of note, this analysis set may be restricted to Phase 1 and Phase 2 participants for analyses on parameters not collected for phase 3a participants.

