Exploratory 4b	COVID-19 with onset at any time after the first dose of study vaccine administration and up to Day 92	ITT + no prior infection (3b & Pooled)	[Last date at risk – Date received 1st dose]+1	No
Exploratory 5a	Severe COVID-19 with onset between Day 36 and Day 92 by specific variant	miITT (3b & Pooled)	[Last date at risk – Date received 1st dose]+1	No
Exploratory 5b	Severe COVID-19 with onset at any time after the first dose of study vaccine administration and up to Day 92	ITT + no prior infection (3b & Pooled)	[Last date at risk – Date received 1st dose]+1	No

\*COVID-19 events will be confirmed, protocol-defined cases. \*\* Where the last date at risk will be defined as COVID-19-event date or censor date, whichever comes first.

(a) Unless specified otherwise, reference to the protocol endpoints is a reference to the Phase 3b endpoints.

Confirmed, protocol-defined COVID-19 cases will be determined by case report form (CRF) data, as confirmed by the blinded Independent Adjudication Committee and adjudicated for severity, with the date of case onset as date of symptom onset and date of positive COVID test date, whichever occurs first. Both protocol-defined and (protocol-defined) severe cases flagged in the CRF will be included in the primary endpoint.

For participants with no covid-event during the time interval the censor date for the last date at risk is whichever of the following comes first:

- Date of completion of Day 92 visit;
- Date of death unrelated to COVID-19;
- Date of receipt of Switchover or receipt of non-study COVID-19 vaccine
- Lost to Follow-up (last known alive date or date of Day 1+91 days, which is earlier).

Section 9.2.2 presents the endpoints and analyses in terms of estimands for primary, secondary and exploratory efficacy analyses.

As a sensitivity analysis of the primary endpoint (Phase 3b only), severe cases and deaths due to COVID-19 will be repeated using all COVID-19 cases from CRF, including those cases that are not confirmed by the blinded Independent Adjudication Committee and with severe or death severity as reported in the CRF.

Day 36 is defined as second dose+7 days (29+7=36 days), and Day 92 is defined as second dose+63 days (29+63=92 days). Another sensitivity analysis of the primary endpoint (Phase 3b only) will be performed using Day 92 visit instead of second dose+63 days.

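### The per-protocol efficacy sets delete anyone who takes an outside COVID-19 vaccine by Day 92, with any earlier case, where the mITT analysis censors; PP VE can shift if uptake differs by arm and changes after a case

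*Protocol*

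**What the plan says.** The Protocol (Synopsis, Analysis Sets, and Section 8.2) excludes from the Phase 3b PP set and the Pooled PP set any participant with early infection "or that receives an off-study COVID-19 vaccine prior to Day 92 (IcEv2"). SAP 4.1 repeats the rule for the PP efficacy sets: "or that receives an non-study COVID-19 vaccine prior to Day 92 (IcEv2"). It then lists "Received non-study COVID-19 vaccine (IcEv2) up to Day 92" among the major deviations that remove a participant. Neither document makes an exception for a case, or for follow-up, that came before the outside vaccination.

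The mITT analysis treats the same event differently. Protocol Table 18 (Section 8.7.2) says to "censor at date of Switchover or non-study vaccination". SAP 6.4 lists "Date of receipt of Switchover or receipt of non-study COVID-19 vaccine" among the censor dates, so earlier time and earlier cases count.

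On the role of the PP set, Protocol 8.7.3.4 says that "the sensitivity analysis will be performed in the Phase 3b PP analysis set". SAP 6.4.1.1 repeats the Phase 3b and Pooled analyses of the primary, severe COVID-19 and COVID-19 death endpoints in the PP sets. Other sensitivity analyses are also planned: the Pooled mITT (Protocol 8.7.1.2 and Table 18), all COVID-19 cases in the CRF, and a version using the Day 92 visit (SAP 6.4 and 7.1).

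**The concern.** The case window is onset "with onset between Day 36 and Day 92 inclusive". A participant with COVID-19 on Day 45 who takes an outside vaccine on Day 80 leaves the PP set together with the case. A participant without an event who is vaccinated outside on Day 85 loses about seven weeks of unaffected follow-up. Selecting on something that may happen after the outcome is a known hazard in time-to-event analysis. If having had COVID-19 changes whether a person later seeks a vaccine, cases and non-cases are deleted at different rates, and the observed case rate in that arm is distorted.

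What is at stake is the reading of the PP result. A gap between PP VE and mITT VE, or agreement between them, could be an artefact of the deletion rule and be taken as evidence for or against the primary result.

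**Working it through.** **The plan's own figure.** Schoenfeld events for HR 0.5 against a null of 0.7, one-sided 0.025, 90% power, 1:1 allocation: 4 × (1.960 + 1.282)² / (ln(0.5/0.7))² = 371.2, so 372. This matches Protocol 8.4.2.

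**When the rule acts.** Protocol 6.8.1 gives no further study doses after an outside vaccine, so anyone vaccinated outside before dose 2 is already out of the mITT set. The deletion specific to PP acts from about Day 29 to Day 92. Protocol 5.2.3 advises waiting at least 28 days after the last study dose, which after dose 2 is about Day 57, inside the case window.

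**Inputs.**
- Window: Day 36 to Day 92, 57 days.
- True VE: 50%. Placebo risk set to give about 372 cases in 16,000.
- Outside uptake u per arm by Day 92: an assumption, 5-25%. No Phase 3b figure is given. The upper end borrows the Phase 3c allowance, a "dropout rate of approximately 20-25% due to the national COVID-19 vaccination campaign in Vietnam".
- θ: the outside-vaccination rate after a case divided by the rate without one, also an assumption.

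**Formula.** With a rare outcome and constant rates over the window, deleting everyone vaccinated by Day 92 multiplies an arm's observed case rate by

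g(u, θ) = [(1−u)^θ − (1−u)] / [(1−θ) × (−ln(1−u)) × (1−u)], and g = 1 when θ = 1.

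PP VE = 1 − 0.5 × g(ARCT-154) / g(placebo).

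**Example: 10% uptake on ARCT-154, 25% on placebo.**
- θ = 0: g = 1.055 and 1.159; PP VE 54.5%.
- θ = 0.5: g = 1.027 and 1.075; PP VE 52.3%.
- θ = 1: g = 1 in both arms; PP VE 50.0%.
- θ = 1.5: g = 0.974 and 0.931; PP VE 47.7%.

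Solving the expected Cox score on a time grid gives 54.4%, 52.2%, 50.0% and 47.7%. Censoring at vaccination gives 50.0% throughout.

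**Range from the Cox calculation** (uptake starting Day 36 or Day 57, θ from 0 to 0.5):
- ARCT-154 15%, placebo 25%: PP VE 51.5-54.2%.
- 10% and 25%: 52.2-56.0%.
- 5% and 25%: 52.9-57.6%.
- Reversed, 25% and 15%: 45.3-48.4%.

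**A 5-point gap.** With uptake over the whole window, 20% against 25% gives 51.6% (θ = 0) or 50.8% (θ = 0.5), and 5% against 10% gives 51.3% or 50.7%. If uptake starts on Day 57, the first 21 of 57 days are free of it. At θ = 0, g is then (0.368 + 0.632 × 0.896)/0.80 = 1.168 at 20% and (0.368 + 0.632 × 0.869)/0.75 = 1.223 at 25%, so PP VE is 1 − 0.5 × 1.168/1.223 = 52.2%.

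**Equal uptake.** VE stays at 49.9-50.0%. At θ = 1, PP keeps 298 of 372 cases at 20% uptake (80%) and 280 of 372 at 25% (75%). Nominal power at those counts is about 83% and 80%. Censoring would keep 334-349 and 324-342, so deletion costs 11-15% and 14-18% more cases than censoring does.

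**COVID-19 death.** A participant who dies cannot be vaccinated afterwards, so θ = 0 by definition, and any difference in uptake between arms shifts PP VE for death. The severe endpoint includes deaths (SAP 6.4.2.1) and inherits part of this.

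**The case against.** Removing a participant for a major deviation is a conventional PP definition. Success is judged only in the Phase 3b mITT set. The design also works against large differences in uptake: people planning off-study vaccination are ineligible (Protocol 5.1.2, criterion 10), the study is observer-blind, participants who ask are reminded of the Switchover design (5.2.3), and outside vaccination is discouraged (6.8.1). Censoring has its own assumption, that uptake is unrelated to infection risk. With censoring, the PP set would differ from the mITT set mainly by eligibility, wrong vaccine, visit windows and undetermined serology. And by the SAP date of 20 July 2023, Phase 3b efficacy had been analysed unblinded (SAP 2.4 and 2.5), so changing a prespecified set now is not purely editorial.

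Most of this stands, and it limits both the weight of the point and the form of the fix. It does not justify discarding valid cases and follow-up that came before the deviation.

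A reader might infer more: that deletion always inflates case rates, that unequal uptake alone biases PP VE, or that the 20-25% describes Phase 3b. None of these is supported. With θ = 1, unequal uptake leaves VE at 50.0%; with θ above 1, rates are deflated and the shift reverses. The 20-25% is a dropout allowance for an active-controlled cohort without Switchover.

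**Conclusion.** The point holds in conditional form. PP efficacy membership depends on an event that can follow the outcome, while the mITT rule for the same event does not discard earlier data. A shift in PP VE needs uptake that differs by arm and uptake that changes after a case; for COVID-19 death only the first is needed. The direction cannot be known in advance.

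Under the assumed uptake the shift at true VE 50% is about 2 points or less for a 5-point gap. For gaps of 10 to 20 points it is about 1.5 to 4 points if uptake halves after a case and about 3 to 8 points if there is none. At true VE 30% the 10- to 20-point-gap scenarios give PP VE of 23.5-40.6%. With equal uptake the cost is precision only. These sizes rest on assumed uptake, constant vaccination rates once uptake starts, and uptake unrelated to underlying infection risk.

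It would be wrong to conclude that the primary result or the 372-event calculation is compromised, or that the whole robustness assessment rests on the PP set. The mITT analysis is untouched, and several other sensitivity analyses are named.

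**What to change.** In SAP 4.1 and 6.4.1.1, run the Phase 3b and Pooled PP efficacy analyses with these participants kept, if otherwise eligible, and censored at the non-study vaccination date, as SAP 6.4 already does for the mITT set. Exclude only those vaccinated outside the study before the at-risk period starts (second dose + 7 days); they contribute no time at risk in any case.

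Because efficacy data were already unblinded when this SAP was written, record the change in SAP Section 7 and report the prespecified whole-participant exclusion alongside as a labelled supplementary analysis. Tabulate outside-vaccine uptake by arm and by whether a case had already occurred, so that a reader can see whether the two conditions for bias are met. At the same time, reconcile the label for this intercurrent event: Protocol Table 16 calls it hypothetical and SAP 9.2.2 calls it treatment policy, while SAP 6.4 censors.

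The cost is one additional analysis, one table and some wording. The vaccination dates are already needed for mITT censoring, so no new data are required. The remaining weakness is that censoring still assumes uptake is unrelated to infection risk.
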